16.33 Correlative Research

16.331 To determine if CTCs of cfDNA at baseline will correlate with prognosis or response to therapy.

16.332 To determine if change in CTCs or cfDNA will correlate with efficacy endpoints.

16.333 To determine if different mutations status of the tumor will affect efficacy endpoints.

16.4 Data & Safety Monitoring:

16.41 Review

The study chair(s) and the study statistician will review the study at least twice a year to identify accrual, adverse event, and any endpoint problems that might be developing. The Mayo Clinic Cancer Center (MCCC) Data Safety Monitoring Board (DSMB) is responsible for reviewing accrual and safety data for this trial at least twice a year, based on reports provided by the MCCC Statistical Office.

16.42 Adverse Event Stopping Rules

The stopping rules specified below are based on the knowledge available at study development. We note that the Adverse Event Stopping Rule may be adjusted in the event of either (1) the study re-opening to accrual or (2) at any time during the conduct of the trial and in consideration of newly acquired information regarding the adverse event profile of the treatment(s) under investigation. The study team may choose to suspend accrual because of unexpected adverse event profiles that have not crossed the specified rule below.

Accrual will be temporarily suspended to this study if at any time we observe events considered at least possibly related to study treatment (i.e. an adverse event with attribute specified as “possible”, “probable”, or “definite”) that satisfy either of the following:

- If 3 or more patients in the first 10 treated patients (30% or higher after first 10 patients) experience at least one grade 4+ adverse event at least possibly related to the study treatment
- If one or more patients in the first 10 treated patients (20% or higher after first 10 patients) experience a grade 5 adverse event at least possibly related to the study treatment

We note that we will review Grade 4 and 5 adverse events deemed “unrelated” or “unlikely to be related”, to verify their attribution and to monitor the emergence of a previously unrecognized treatment-related adverse event.

16.7 Inclusion of Women and Minorities

16.71 Availability

This study will be available to all eligible patients, regardless of race, gender, or ethnic origin.

16.72 Differential effects

There is no information currently available regarding differential effects of this regimen in subsets defined by race, gender, or ethnicity, and there is no reason to expect such differences to exist. Therefore, although the planned analysis will, as always, look for differences in treatment effect based on racial and gender groupings, the sample size is not increased in order to provide additional power for subset analyses.

16.73 Mayo Clinic Population

Based on prior MC studies involving similar disease sites, we expect about 4 % of patients will be classified as minorities by race and about 50 % of patients will be women. Expected sizes of racial by gender subsets for patients registered to this study are shown in the following table:

Accrual Targets			
Ethnic Category	Sex/Gender		
	Females	Males	Total
Hispanic or Latino	1	1	2
Not Hispanic or Latino	13	13	26
Ethnic Category: Total of all subjects	14	14	28
Racial Category			
American Indian or Alaskan Native	0	0	0
Asian	0	0	0
Black or African American	1	1	2
Native Hawaiian or other Pacific Islander	0	0	0
White	13	13	26
Racial Category: Total of all subjects	14	14	28

Ethnic Categories: **Hispanic or Latino** – a person of Cuban, Mexican, Puerto Rican, South or Central American, or other Spanish culture or origin, regardless of race. The term “Spanish origin” can also be used in addition to “Hispanic or Latino.”

Not Hispanic or Latino

Racial Categories:	
American Indian or Alaskan Native – a person having origins in any of the original peoples of North, Central, or South America, and who maintains tribal affiliations or community attachment.
 
Asian – a person having origins in any of the original peoples of the Far East, Southeast Asia, or the Indian subcontinent including, for example, Cambodia, China, India, Japan, Korea, Malaysia, Pakistan, the Philippine Islands, Thailand, and Vietnam. (Note: Individuals from the Philippine Islands have been recorded as Pacific Islanders in previous data collection strategies.)
 
Black or African American – a person having origins in any of the black racial groups of Africa. Terms such as “Haitian” or “Negro” can be used in addition to “Black or African American.”
 
Native Hawaiian or other Pacific Islander – a person having origins in any of the original peoples of Hawaii, Guam, Samoa, or other Pacific Islands.
 
White – a person having origins in any of the original peoples of Europe, the Middle East, or North Africa.

---------------------------	---

17.0 Pathology Considerations/Tissue Biospecimens: None

18.0 Records and Data Collection Procedures

18.1 Submission Timetable

Data submission instructions for this study can be found in the Data Submission Schedule.

18.2 Event monitoring

See [4.0 Test Schedule](#) and Data Submission Schedule (DSS) for the event monitoring schedule.

18.3 CRF completion

This study will use Medidata Rave for remote data capture (rdc) of all study data.

18.4 Site responsibilities

Each site will be responsible for insuring that all materials contain the patient's initials, MCCC registration number, and MCCC protocol number. Patient's name must be removed.

18.5 Supporting documentation

This study requires baseline supporting documentation of histologic diagnosis and staging of genetic mutations which includes the most recent tumor tissue biopsy pathology report. To submit these materials, they can be uploaded into the Supporting Documentation form in Medidata Rave®. These reports should be submitted within 21 days of registration.

This study requires supporting documentation for evidence of response to study therapy and progression after study therapy. Documentation of tumor genetic mutations is requested at any time, if available.

18.6 Labelling of materials

Each site will be responsible for insuring that all materials contain the patient's initials, MCCC registration number, and MCCC protocol number. Patient's name must be removed.

18.7 Incomplete materials

Any data entered into a form will result in that form being marked as "received." However, missing data in each form will be flagged by edit checks in the database.

18.8 Overdue lists

A list of overdue materials is automatically available to each site at any time. In addition, a list of overdue materials and forms for study patients will be generated monthly. The listings will be sorted by location and will include the patient study registration number. The appropriate co-sponsor/participant will be responsible to obtain the overdue material.

18.9 Corrections forms

If a correction is necessary the QAS will query the site. The query will be sent to the appropriate site to make the correction in the database and respond back to the QAS.

19.0 Budget

19.1 Costs charged to patient

Routine clinical care costs will be the responsibility of the patient and/or the patient's insurance company. This responsibility includes costs associated with surgery and with the administration of standard chemotherapy (carboplatin/paclitaxel or FOLFOX), and radiotherapy. These drugs are commercially available and will be the responsibility of the patient and/or the patient's insurance company.

19.2 Tests to be research funded

- FTD/TPI (TAS-102) will be provided by Taiho Oncology
- Correlative studies
- Collection, processing and storage of blood for research.

19.3 Other considerations

Taiho Oncology will provide a grant to Mayo Clinic to help with costs for the conduct of this study.

Appendix I ECOG Performance Status

ECOG PERFORMANCE STATUS*	
Grade	ECOG
0	Fully active, able to carry on all pre-disease performance without restriction
1	Restricted in physically strenuous activity but ambulatory and able to carry out work of a light or sedentary nature, e.g., light house work, office work
2	Ambulatory and capable of all selfcare but unable to carry out any work activities. Up and about more than 50% of waking hours
3	Capable of only limited selfcare, confined to bed or chair more than 50% of waking hours.
4	Completely disabled. Cannot carry on any selfcare. Totally confined to bed or chair.
5	Dead

*As published in Am. J. Clin. Oncol.:

The ECOG Performance Status is in the public domain therefore available for public use. To duplicate the scale, please cite the reference above and credit the Eastern Cooperative Oncology Group, Robert Comis M.D., Group Chair.

From http://www.ecog.org/general/perf_stat.html

Appendix II Patient Medication Diary

Name _____ **Study ID Number** _____

Please complete this diary on a daily basis. Write in the number of pills that you took in the appropriate “Day” box.

On the days that you do not take any study drug, please write in “0”. If you forget to take your dose, please write in “0”, but remember to take your prescribed dose at the next regularly scheduled time.

Take your pills twice per day with water within one hour after a meal.

If you experience any health/medical complaints or take any medication other than FTD/TPI (TAS-102), please record this information.

Week of: _____

Study Drug	Day 1		Day 2		Day 3		Day 4		Day 5	
FTD/TPI (TAS-102)	AM	PM								
15 mg tablets										
20 mg tablets										

Week of: _____

Do not take any TAS-102 this week

Week of: _____

Study Drug	Day 8		Day 9		Day 10		Day 11		Day 12	
FTD/TPI (TAS-102)	AM	PM	AM	PM	AM	PM	AM	PM	AM	PM
15 mg tablets										
20 mg tablets										

Week of: _____

Do not take any FTD/TPI (TAS-102) this week

Week of: _____

Do not take any FTD/TPI (TAS-102) this week

Remember to bring this diary with you to your next appointment along with any FTD/TPI pill bottles (full, empty, or partially filled).

Patient signature: _____

Date: _____

Health or medical complaints during this time:

Other medications or supplements taken during this time:

Use a separate sheet of paper if more space is needed.

My next scheduled visit is: _____

If you have any questions, please call:

Number of pills returned _____
Discrepancy Yes /No

Study Coordinator Use Only

Number of vials returned:

Verified by _____

Date _____

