4.0 Study Schedules

4.1 Test schedule

Tests and Procedures	Screening prior to registration	Active Treatment			End of Treatment	
		D1 of each cycle	D8 of Cycle 1 only	Every 2 cycles	End of Treatment	Safety follow up: 30 days post treatment
window		±7 days	±3 days	±7 days	±7 days	±7 days
History and exam, Wt, PS	X	X	X		X	X
Height	X					
Adverse event assessment	X	X	X		X	X
Pregnancy test ¹	X					
Hematology: CBC with differential	X	X	X		X	X
Chemistry ²	X	X	X		X	X
CA19-9 ³		X		X ⁴	X	
Tumor imaging - CT (chest, abdomen, pelvis) or CT (chest) and MRI (abdomen, pelvis)	X ⁵			X ⁶	X	
Research blood specimens ^{7,R}		X			X	
Patient Medication Diary (Appendix II) ⁸		X				

Cycle = 28 days; R=Research funded

¹ For persons of childbearing potential only. Must be done ≤7 days prior to registration.

² Chemistry: Na, K, albumin, AST, ALT, alkaline phosphatase, total and direct bilirubin, creatinine

³ Baseline prior to Cycle 1, Day 1, then every two cycles or as clinically indicated

⁴ To be performed ≤7 days prior to planned Day 1 of odd numbered cycles (Cycle 3, 5, 7 etc) or as clinically indicated

⁵ Can be performed ≤28 days prior registration

⁶ To be performed ≤7 days prior to planned Day 1 of odd numbered cycles (Cycle 3, 5, 7 etc) or as clinically indicated

⁷ Research blood specimens to be collected on Cycle 1 Day 1 (or any time between registration and Cycle 1 Day 1), Cycle 3 Day 1 and end of treatment (see [Section 14.0](#))

⁸ The diary must begin the day the patient starts taking the medication and must be completed per protocol and returned to the treating institution

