7.1 Treatment Schedule

Use actual weight or estimated dry weight if fluid retention. BSA needs to be rounded to 2 decimal places. The study medication needs to be stored at the room temperature.

FTD/TPI (TAS-102) is administered in 28-day cycle. The starting dose of FTD/TPI (TAS-102) is 35 mg/m². The study drug will be administered on Days 1-5 and 8-12 of 28-day cycle. The treatment regimen consists of following:

Agent	Route	Day	Starting Dose
FTD/TPI (TAS-102)	PO	1-5	35 mg/m ² /dose twice daily
None		6-7	No treatment
FTD/TPI (TAS-102)	PO	8-12	35 mg/m ² /dose twice daily
None		13-28	No treatment

The study drug dose calculation based on BSA is as follows:

FTD/TPI (TAS-102) dose (twice daily)	BSA (m ²)	Dosage in mg (twice daily)	Tablets per dose	
			15 mg	20 mg
35 mg/m ²	<1.07	35	1	1
35 mg/m ²	1.07-1.22	40	0	2
35 mg/m ²	1.23-1.37	45	3	0
35 mg/m ²	1.38-1.52	50	2	1
35 mg/m ²	1.53-1.68	55	1	2
35 mg/m ²	1.69-1.83	60	0	3
35 mg/m ²	1.84-1.98	65	3	1
35 mg/m ²	1.99-2.14	70	2	2
35 mg/m ²	2.15-2.29	75	1	3
35 mg/m ²	≥2.30	80	0	4

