8.3 Dose Modifications at the Time of Retreatment (Beginning of new cycle)

8.31 The dose modification guidelines for FTD/TPI (TAS-102) for non-specified adverse events on **Day 1** of each cycle of the treatment is mentioned below:

CTCAE Adverse Events ¹	Action for FTD/TPI (TAS-102)
Grade 1 or 2	Treat as scheduled
Grade 3 or 4	Delay Treatment until resolve to \leq Grade 2. Reduce the dose by one dose level.

¹ Except for alopecia, clinically insignificant laboratory abnormalities, and inadequately treated nausea, vomiting and diarrhea.

8.32 The dose modification guidelines for FTD/TPI (TAS-102) for specified adverse events on **Day 1** of each cycle of the treatment is mentioned below:

CTCAE { Adverse Events	Action for FTD/TPI (TAS-102)
Neutrophil count decreased $<1,500/\text{mm}^3$	Delay treatment by 1 week Reduce dose by one dose level for next treatment only if febrile neutropenia or uncomplicated Grade 4 neutropenia occurs that requires more than one week delay in start of next cycle
Platelet count decreased $<75,000/\text{mm}^3$	Delay treatment by 1 week Reduce dose by one dose level for next treatment only if Grade 4 thrombocytopenia occurs that requires more than one week delay in start of next cycle

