11.1 Schedule of Evaluations

For the purposes of this study, patients should be reevaluated every 8 weeks. In addition to a baseline scan, confirmatory scans should also be obtained 8 weeks following initial documentation of objective response.

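### The patient diary prints a surplus no-drug week between the Day 1-5 and Day 8-12 tables, in the week when Section 7.1 requires dosing

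*Combined protocol and SAP*

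**What the plan says.** Section 7.1 gives the schedule twice, in text and in a table. The text reads "FTD/TPI (TAS-102) is administered in 28-day cycle" and "The study drug will be administered on Days 1-5 and 8-12 of 28-day cycle". The table shows no treatment on Days 6-7 and Days 13-28. Section 1.4 gives the same dosing days, and the note under the Section 4.1 test schedule gives the same cycle length.

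The Appendix II diary is the form on which patients record their doses. It has five blocks, each with its own 'Week of' line, in this order:

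1. a table labelled Day 1 to Day 5;
2. "Do not take any TAS-102 this week";
3. a table labelled Day 8 to Day 12;
4. "Do not take any FTD/TPI (TAS-102) this week";
5. the same no-drug sentence again.

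The diary is required. Footnote 8 of Section 4.1 says that it "must be completed per protocol and returned to the treating institution".

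**The concern.** Five weekly blocks do not fit a 28-day cycle, and the extra one falls where it does most harm. Two days separate the dosing courses in Section 7.1, yet the diary puts a full no-drug week there. The form also contradicts itself, because the table after the off-week is still labelled Day 8 to Day 12.

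The drug is a cytotoxic that patients take at home under Section 7.2. A line on a required patient form that withholds it in a dosing week is an operative instruction, even though the treatment section is clear. If the second course slips by a week and the next cycle starts on time, the patient has less time to recover before re-dosing. Section 8.32 shows that recovery matters: when Day 1 neutrophils are below 1,500/mm³ the action is "Delay treatment by 1 week". Table 1 in Section 1.2 reports 38% Grade 3-4 neutropenia with the drug. That figure comes from the standard schedule. It shows why recovery time matters and does not measure what a shorter rest would do.

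**Working it through.** **Inputs.** Cycle length 28 days (Sections 7.1 and 4.1). Drug on Days 1-5 and 8-12, none on Days 6-7 and 13-28 (Section 7.1). Five weekly blocks, two with dosing tables and three without drug (Appendix II). Day 1 visit window ±7 days (Section 4.1).

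**1. The schedule in Section 7.1.** 5 + 2 + 5 + 16 = 28 days, and 28 / 7 = 4 weeks. The week of a given day is floor((day − 1) / 7) + 1. Days 1-5 fall in week 1 and Days 8-12 in week 2. The plan is therefore two consecutive dosing weeks, then two weeks off (Days 15-28). It is internally consistent.

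**2. The diary.** 5 blocks × 7 = 35 days, which is 35 − 28 = 7 days too many. Block *i* covers calendar days 7(*i* − 1) + 1 to 7*i*:

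| Block | Diary content | Calendar days in printed order | Section 7.1 for those days |
|---|---|---|---|
| 1 | Table, Day 1 to Day 5 | 1-7 | Drug on 1-5 |
| 2 | No drug | 8-14 | Drug on 8-12 |
| 3 | Table, Day 8 to Day 12 | 15-21 | No drug |
| 4 | No drug | 22-28 | No drug |
| 5 | No drug | 29-35 | Next cycle |

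The count does not depend on page layout. In any order, two dosing weeks plus three off-weeks make 35 days.

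**3. A patient who follows the blocks in order.** Drug is taken on Days 1-5 and 15-19, so 5 of the 10 required dosing days match.

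- Gap between the two courses: Days 6-14, 14 − 6 + 1 = 9 days, against 7 − 6 + 1 = 2 planned.
- Rest before a next cycle on Day 29: Days 20-28, 28 − 20 + 1 = 9 days, against 28 − 13 + 1 = 16 planned.
- Dosing days per cycle: 10 in 28 in both cases.

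**4. If the clinic also lets the cycle run to 35 days.** Rest is Days 20-35, 35 − 20 + 1 = 16 days. The next Day 1 is Day 36 = 29 + 7, the outer edge of the window. Relative planned intensity is (10/35) / (10/28) = 28/35 = 0.80. This needs a second departure beyond the misread form.

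**5. With the second block removed.** 4 × 7 = 28 days: week 1 has Days 1-5, week 2 has Days 8-12, and weeks 3 and 4 (Days 15-28) have no drug. This matches Section 7.1 exactly.

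**The case against.** The best reply is that the form largely corrects itself and that the clinic would catch a slip. The 'Week of' lines are blank, so the diary does not itself assign the surplus block to Days 8-14. The second table carries the right day numbers, and the recording instruction ("Write in the number of pills that you took in the appropriate") goes on to name a Day box. Section 7.2 has patients told to keep to the schedule and to return unused tablets each cycle. Section 7.3 keeps treatment away from local doctors. Section 4.1 has a visit on Day 8 of Cycle 1 and blood counts on Day 1 of every cycle, so a patient with unrecovered counts would be held under Section 8.32. On this view the defect is a visible slip on one form and is minor.

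Much of this is fair. The harm is limited to patients who follow the block order, and the count check is a real safeguard against re-dosing too early. The safeguards are still partial:

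- The Day 8 visit occurs in Cycle 1 only. With its ±3-day window it can fall on Days 5-7, before the second course is due.
- A patient who shifts the second course still takes all ten days of tablets and fills in every Day box. The coordinator's pill count would then show no discrepancy. Only the handwritten week dates would reveal the shift.
- Reading the extra block as Days 6-7 is strained, because it has its own weekly header and refers to a week.

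Scan timing also needs care. Section 11.1 says "For the purposes of this study, patients should be reevaluated every 8 weeks", while footnote 6 of Section 4.1 ties imaging to the planned start of odd-numbered cycles. With 28-day cycles the two agree (2 × 28 = 56 days, or 8 weeks). They separate only if cycles run to 35 days (2 × 35 = 70 days, or 10 weeks). Scans need not move if the 8-week rule is kept.

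**Conclusion.** The concern holds. The diary contains one weekly block too many, and in printed order that block withholds drug in the week containing Days 8-12. For a patient who follows the blocks, the second course falls on Days 15-19. If the next cycle starts on Day 29, rest before re-dosing is 9 days instead of 16. The 0.80 intensity figure applies only if the cycle is also allowed to run to 35 days.

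This rests on each 'Week of' block meaning seven days. It does not assume that any patient was misled, which the protocol cannot show. No size is claimed for an effect on blood counts, because no data on a shorter rest are given. The definition of the 16-week endpoint, the 25 evaluable patients, the power table and the decision rule are all unaffected. The error should be fixed because it is a wrong dosing instruction on a required patient form and is easily removed.

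**What to change.** Delete the no-drug block between the two dosing tables. Alternatively, replace it with a short line under the first table, without its own weekly header, saying that no study drug is taken on Days 6 and 7. The four remaining blocks then match Section 7.1. Submit the revised form to the IRB and reissue it. If diaries have already been used, check their 'Week of' dates for second courses taken a week late.

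The cost is a small edit to one appendix, an IRB submission and, where needed, a check of returned diaries. Design, sample size and analysis do not change.

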Appendix III Taiho Tables for Frequency for Serious Adverse Drug Reactions for TAS-102

The baseline frequency for serious adverse drug reactions by MedDRA System Organ Class (Version 18.0) and preferred term in patients receiving FTD/TPI (TAS-102) monotherapy^a is as below (data taken from TAS-102 Global Investigator's Brochure Ver 7.0 11Oct2016):

MedDRA SOC	Baseline ^b (N=769), n (%)
Preferred Term	
Total Serious Related Advere Events	60 (7.8)
Blood and lymphatic system disorders	32 (4.2)
Anaemia	10 (1.3)
Disseminated intravascular coagulation	1 (0.1)
Febrile neutropenia	18 (2.3)
Leukopenia	2 (0.3)
Neutropenia	5 (0.7)
Pancytopenia	1 (0.1)
Thrombocytopenia	1 (0.1)
Gastrointestinal disorders	16 (2.1)
Abdominal pain	4 (0.5)
Anal fistula	1 (0.1)
Ascite	1 (0.1)
Colitis	2 (0.3)
Constipation	1 (0.1)
Diarrhoea	3 (0.4)
Ileus	2 (0.3)
Nausea	2 (0.3)
Pancreatitis acute	1 (0.1)
Subileus	1 (0.1)
Vomiting	5 (0.7)
General disorders and administration site conditions	5 (0.7)
Fatigue	3 (0.4)
General physical health deterioration	1 (0.1)
Malaise	1 (0.1)
Hepatobiliary disorders	2 (0.3)
Cholangitis	1 (0.1)
Liver disorder	1 (0.1)
Infections and infestations	11 (1.4)
Bacteraemia	1 (0.1)

MedDRA SOC	Baseline ^b
Preferred Term	(N=769), n (%)
Infections and infestations (continued)	11 (1.4)
Biliary tract infection	1 (0.1)
Cellulitis	1 (0.1)
Endophthalmitis	1 (0.1)
Enteritis infections	1 (0.1)
Lower respiratory tract infection	1 (0.1)
Pelvic infection	1 (0.1)
Pneumonia	4 (0.5)
Pneumonia klebsiella	1 (0.1)
Sepsis	1 (0.1)
Septic shock	1 (0.1)
Urinary tract infection	2 (0.3)
Investigations	4 (0.5)
Blood lactate dehydrogenase increased	1 (0.1)
Haemoglobin decreased	1 (0.1)
Neutrophil count decreased	1 (0.1)
Platelet count decreased	1 (0.1)
Weight decreased	1 (0.1)
White blood cell count decreased	2 (0.3)
Metabolism and nutrition disorders	6 (0.8)
Decreased appetite	4 (0.5)
Dehydration	3 (0.4)
Hypokalaemia	1 (0.1)
Hyponatraemia	1 (0.1)
Renal and urinary disorders	1 (0.1)
Acute kidney injury	1 (0.1)
Respiratory, thoracic and mediastinal disorders	1 (0.1)
Pulmonary embolism	1 (0.1)

^aTAS-102 studies investigating 35 mg/m²/dose monotherapy in patients with colorectal cancer.

^bOnly includes serious adverse events from protocols completed as of 24 July 2016: J001-10040010, J003-10040030, J004-10040040, TPU-TAS-102-101, TPU-TAS-102-102, TPU-TAS-102-103, TPU-TAS-102-104, TPU-TAS-102-108, TPU-TAS-102-301.

Further adverse events (>5%) in the RE COURSE study are mentioned in section 1.2.

The most frequently reported adverse events (>10% in either pooled treatment group) reported for patients in the randomized studies (J003-10040030 and TPU-TAS-1-2-301) is as follows (data taken from TAS-102 Global Investigator's Brochure Ver 7.0 11Oct2016):

MedDRA SOC Preferred Term	Studies J003-10040030 and TPU-TAS-102-301 Combined			
	TAS-102 (N=646), n (%)		Placebo (N=322), n (%)	
	All Grades	Grade ≥ 3	All Grades	Grade ≥ 3
Any adverse event	635 (98.3)	448 (69.3)	299 (92.9)	146 (45.3)
Blood and lymphatic system disorder	311 (48.1)	195 (30.2)	29 (9.0)	11 (3.4)
	216 (33.4)	88 (13.6)	22 (6.8)	7 (2.2)
	156 (24.1)	107 (16.6)	0	0
Gastrointestinal disorders	502 (77.7)	83 (12.8)	195 (60.6)	37 (11.5)
	101 (15.6)	12 (1.9)	46 (14.3)	10 (3.1)
	92 (14.2)	1 (0.2)	44 (13.7)	3 (0.9)
	213 (33.0)	23 (3.6)	45 (14.0)	1 (0.3)
	331 (51.2)	15 (2.3)	79 (24.5)	3 (0.9)
	186 (28.8)	15 (2.3)	52 (16.1)	1 (0.3)
General disorders and administration site conditions	457 (70.7)	77 (11.9)	168 (52.2)	38 (11.8)
	97 (15.0)	18 (2.8)	30 (9.3)	8 (2.5)
	246 (38.1)	25 (3.9)	82 (25.5)	16 (5.0)
	67 (10.4)	2 (0.3)	31 (9.6)	3 (0.9)
	114 (17.6)	6 (0.9)	44 (13.7)	2 (0.6)
Investigations	399 (61.8)	216 (33.4)	132 (41.0)	44 (13.7)
	53 (8.2)	9 (1.4)	34 (10.6)	8 (2.5)
	64 (9.9)	21 (3.3)	41 (12.7)	14 (4.3)
	78 (12.1)	24 (3.7)	27 (8.4)	11 (3.4)
	85 (13.2)	21 (3.3)	9 (2.8)	3 (0.9)
	229 (35.9)	142 (22.0)	2 (0.6)	0
	125 (19.3)	18 (2.8)	7 (2.2)	0
	232 (35.9)	87 (13.5)	3 (0.9)	0
Metabolism and nutrition disorders	319 (49.4)	58 (9.1)	123 (38.2)	29 (9.0)
	278 (43.0)	24 (3.7)	97 (30.1)	15 (4.7)
Respiratory, thoracic and mediastinal disorders	169 (26.2)	33 (5.1)	86 (26.7)	18 (5.6)
	63 (9.8)	2 (0.3)	33 (10.2)	2 (0.6)
	63 (9.8)	16 (2.5)	34 (10.6)	10 (3.1)
